## 2 Sample Size

In the Phase 2a trial, IGA response rates of 21.6% and 11.8% were observed for DS107 and placebo respectively resulting in a difference in response rates of 9.8%. Due to the prolonged treatment period of 16 weeks, a clinically relevant difference in IGA response rates of 15% was expected for the current study.

Assuming a placebo response rate of 12% and a true response rate difference of 15% at Week 16 and using a two-sided Chi-Square test on a significance of 5%, then 220 evaluable patients (110 patients per treatment arm) will be needed for 80% power to detect this difference as statistically significant. As the following table shows, the number of patients needed for the discovery of a 15% response rate difference depends also on the placebo response rate shown in the left column of the table as decimal numbers:

**Number of patients per study group required under the assumptions as follows**  
**Chi-square test, 2 x 2 table, Two Proportions, two-sided.**  
**Sample Size 1 as a function of H1: Proportion 1 and Power.**  
**H1: Proportion 2 - Proportion 1=0,15 Significance Level=0,05 Sample Size 2 / Sample Size 1=1**

H1: Proportion 1 = Response Rate Placebo	Power		
	0,7	0,8	0,9
0,06	63,4	80,3	107,0
0,08	71,2	90,2	120,3
0,10	78,6	99,6	132,8
0,12	85,5	108,4	144,6
0,14	92,0	116,6	155,6
0,16	98,0	124,3	165,9
0,18	103,6	131,4	175,4
0,20	108,8	138,0	184,2

It was assumed that similar estimations apply to the primary endpoint EASI-75.

### 3 Analysis Populations

The assignment of individual patients to the analysis sets will be determined by the members of the BDRM. The patients will be assigned to the following analysis sets before unblinding:

1. Enrolled Set: The Enrolled Set consists of all patients who sign informed consent.
2. Screen Failures: Screen Failures are patients from the Enrolled Set who do not meet the eligibility requirements and are withdrawn from the study prior to randomisation.
3. Randomised Set: The Randomised Set consists of all patients who are randomised to the study.
4. Safety Analysis Set (SAS): The Safety Analysis Set (SAS) consists of all patients who received at least one dose of the medication. SAS is the analysis population for all safety endpoints. Analysis will be done according to the actual treatment patients received.
5. Full Analysis Set (FAS): The Full Analysis Set (FAS) consists of all patients who were randomised to the study and received at least one dose of study medication. FAS is the primary analysis population for efficacy endpoints. Analysis will be done according to the treatment patients were randomised to.
6. Per-Protocol Set (PPS): The Per Protocol Set (PPS) is the subset of FAS who completed the study without any major violations. Protocol violations will be assessed for each patient in a blinded fashion prior to database lock at a Blind Data Review Meeting (BDRM), and the PPS will also be finalised during this meeting. PPS is a supportive analysis population for efficacy endpoints. Analysis will be done according to the treatment patients were randomised to.

For PPS the primary endpoint will only be evaluated in an exploratory sense.

## 4 Data Handling

### 4.1 General

#### 4.1.1 Data sources

Most of the data collected in connection with this trial are recorded in an eCRF (electronic Case Report Form). The diary data (NRS, AIS, IMP compliance etc) is recorded in the IRT system. All patient data will be entered by the investigator. Details can be found in the data handling manual for this study. The entered data are subjected to plausibility checks. These are detailed in the data validation plan for this study.

#### 4.1.2 Coding

The process of coding is performed according to the *AMS* internal Coding SOP and relevant Coding guidelines (e.g. 'MedDRA Points to consider' / 'Best Practices for the use of the WHO Drug Dictionaries').

The data to be coded is extracted into a coding database where the coding is performed. Details of the coding database, the items to be coded, the frequency of coding and the 'MedDRA' version used for coding of diseases and adverse events and the WHO DD version used for coding of medications and the update frequency of the dictionaries are defined in the Coding Specification.

#### 4.1.3 Visits

The analysis visits and points in time will be presented as documented in the database.

#### 4.1.4 Baseline value

The last non-missing value prior to first treatment will be referred to as baseline value and will be used for change from baseline calculations.

#### 4.1.5 Missing values

If only the day is not known completely, for onset dates or start dates missing day information will be assumed as the 1st. If both day and month are missing, the 1st January will be used. For stop dates missing day information will be imputed as the last of the month, if both day and month are missing, the 31st December will be used.

However, if for AEs it is not clear whether the event started prior to or in the treatment period, the onset at day of first treatment will be assumed.

If it is not clear due to a missing or incomplete stop date of a medication whether the medication was taken at least once after the first treatment of the patient, a stop date after the day of the first patient visit will be assumed. The medication will therefore be classified as "concomitant medication". If it is not clear due to a missing or incomplete start date of a medication whether the medication was taken at least once before the first treatment of the patient, a start date before the day of the first patient visit will be assumed. The medication will therefore be classified as "previous medication" (cf. section 4.2.14).

Data from patients who prematurely terminate the trial will be used to the maximum extent possible.

The primary statistical analysis assumes “Missing At Random (MAR)” when handling missing data. The treatment effect obtained under the MAR assumption is essentially that which could have been reached if all patients had fully adhered to treatment or, in other words, the effect a patient may expect if they take the medication as directed. This is sometimes known as the ‘de jure’ or ‘efficacy’ estimand. Due to the lack of perfect adherence in practice, the ‘de facto’ or effectiveness treatment effect will also be estimated. This estimand includes assumptions regarding the treatment effects that could be expected to occur when patients discontinue treatment. The jump to reference method described by Carpenter et al. (2013) will be used to estimate the de facto estimand, using the placebo arm as the reference. This is based on the assumption that patients who discontinue from study drug have no alternative oral treatment option suitable for longer-term use and so their responses are likely to revert to those of the placebo group. An additional sensitivity analysis will evaluate patients who received rescue medication as treatment failures from the visit onwards where rescue treatment started. The sensitivity analyses for missing data will be performed on the FAS only.

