### 9.2.15 Rescue Treatment

If medically necessary (ie, to control intolerable AD symptoms), rescue treatment for AD may be provided to study patients at the discretion of the investigator. If possible, investigators should avoid administration of rescue treatments before Week 4 due to the expected time to onset of treatment-response following DS107 treatment.

For the purpose of efficacy analysis, patients who receive rescue treatment during the study treatment period will be considered treatment failures from the time rescue treatment is used.

Topical corticosteroids or calcineurin inhibitors may be used for rescue, but should be reserved for problem areas only, eg, face, neck, intertriginous and genital areas, etc. If a patient receives rescue treatment with systemic corticosteroids or non-steroidal systemic immunosuppressive drugs (cyclosporine, methotrexate, mycophenolate mofetil, azathioprine, etc.) study treatment will be immediately discontinued.

Investigators should make every attempt to conduct efficacy and safety assessments (eg, disease severity scores, safety labs) immediately before administering any rescue treatment.

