### 6.1 Primary Endpoint Evaluation

The primary endpoint variables will be:

- the proportion of patients achieving an vIGA-ADTM score of 0 (clear) or 1 (almost clear) and a decrease of at least 2 points in vIGA-ADTM from baseline to Week 16.
- the proportion of patients achieving EASI-75 ( $\geq 75\%$  improvement from baseline) at Week 16.

Both primary endpoints will be analysed using a Generalised Linear Mixed Model (GLMM) with treatment arm, visit, their interaction treatment-by-visit, and baseline vIGA-ADTM value as factors, and with patient as random effect; this model will especially be used to estimate missing data and the treatment effects at Week 16 taking missing data into account. The primary analysis will be based on the FAS, and repeated for the PPS as a supportive sensitivity analysis. Success in either of the primary endpoints denotes successful proof of efficacy.

If rescue medication is used, the patient will be specified as a non-responder from the time the rescue is used.

The handling of missing data in regards with primary statistical analysis and further sensitivity analysis using the jump to reference method to estimate the de facto estimand and analysing patients who received rescue medication as treatment failures are described in section 4.1.5.

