EASI-75 score				
14.2.1.9	EASI score by visit	FAS	Descriptive statistics by visit	T3a
14.2.1.10	EASI score by visit and subgroup	FAS	Descriptive statistics by visit and subgroup	T3a
14.2.1.11	EASI-75 response by visit	FAS	Descriptive statistics by visit	T4a
14.2.1.12	EASI-75 response by visit and subgroup	FAS	Descriptive statistics by visit and subgroup	T4a
14.2.1.13	EASI-75 response from baseline to week 16 (GLMM)	FAS	Proportion of patients achieving EASI-75 ( $\geq 75\%$ improvement from baseline) at Week 16 using a Generalised Linear Mixed Model	T6.1 T6.2

14.2.1.13.1	EASI-75 response from baseline to week 16 (GLMM)	PPS	Proportion of patients achieving EASI-75 ( $\geq 75\%$ improvement from baseline) at Week 16 using a Generalised Linear Mixed Model	T6.1 T6.2
14.2.1.14	EASI-75 response from baseline to week 16 (GLMM) by subgroup	FAS	Proportion of patients achieving EASI-75 ( $\geq 75\%$ improvement from baseline) at Week 16 using a Generalised Linear Mixed Model by subgroup	T6.1 T6.2
14.2.1.15	Sensitivity analysis of EASI-75 response from baseline to week 16 (de facto estimand)	FAS	Jump to reference method to estimate the de facto estimand	T7.1 T7.2
14.2.1.16	Sensitivity analysis of EASI-75 response from baseline to week 16 (rescue medication)	FAS	Patients who received rescue medication will be evaluated as treatment failures	T6.1 T6.2
14.2.2	Secondary Endpoints			
14.2.2.1	vIGA-ADTM score			
14.2.2.1.1	vIGA-AD TM score proportion from baseline to week 4, 8, 12, 18, 20 (GLMM)	FAS	Proportion of patients achieving an vIGA-AD TM score of 0 (clear) or 1 (almost clear) and a decrease of at least 2 points in vIGA-AD TM from baseline to Week 4, 8, 12, 18 and 20 using a Generalised Linear Mixed Model	T6.1 T6.2
14.2.2.1.2	Change in vIGA-AD TM score proportion at follow-up (GLMM)	FAS	Change in proportion of patients achieving an vIGA-AD TM score of 0 (clear) or 1 (almost clear) and a decrease of at least 2 points in vIGA-AD TM from Week 16 to Week 18 and 20 using a Generalised Linear Mixed Model	T6.1 T6.2
14.2.2.1.3	Change in vIGA-AD TM score from baseline to week 4, 8, 12, 16, 18, 20 (MMRM)	FAS	Change in vIGA-AD TM score from baseline to week 4, 8, 12, 16, 18, 20 using Mixed Model with Repeated Measures	T8.1 T8.2

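### At Week 16 the rescue sensitivity analysis uses, in effect, the rescue rule already in the primary analysis, so it says almost nothing about robustness to that rule

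*SAP*

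**What the plan says.** SAP 6.1 gives the rule for both primary endpoints: "If rescue medication is used, the patient will be specified as a non-responder from the time the rescue is used". Protocol 12.8.2 carries the same sentence, and protocol 9.2.15 applies the rule to efficacy analysis generally: "patients who receive rescue treatment during the study treatment period will be considered treatment failures from the time rescue treatment is used".

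SAP 4.1.5, following protocol 12.8.2, then lists a further analysis: "An additional sensitivity analysis will evaluate patients who received rescue medication as treatment failures from the visit onwards where rescue treatment started". SAP 8 allots it tables 14.2.1.8 (vIGA-AD) and 14.2.1.16 (EASI-75), with the content description "Patients who received rescue medication will be evaluated as treatment failures". Both use the FAS and mock tables T6.1 and T6.2, as do the primary tables 14.2.1.5 and 14.2.1.13.

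The same part of the SAP interprets the primary result: "The treatment effect obtained under the MAR assumption is essentially that which could have been reached if all patients had fully adhered to treatment". It calls this the de jure, or efficacy, estimand. The other missing-data analysis is jump to reference, justified on the premise that "patients who discontinue from study drug have no alternative oral treatment option suitable for longer-term use". Protocol 9.2.15 permits topical rescue on limited areas. After systemic rescue, "study treatment will be immediately discontinued".

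**The concern.** A sensitivity analysis is informative only if it changes an assumption that the primary analysis makes. Here the analysis labelled as the rescue sensitivity analysis appears to repeat the primary coding. Two tables that agree with the primary almost by definition could then be read as support for both primary endpoints.

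The interpretation is affected too. Scoring rescue as failure is a composite strategy: rescue becomes part of the outcome. An effect under full adherence is a hypothetical quantity. If rescue differs between arms, the two need not agree, and the plan as written does not show by how much they differ.

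**Working it through.** **1. The rules side by side (binary responder endpoint, FAS, GLMM)**

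| | Primary (SAP 6.1, protocol 12.8.2) | Sensitivity (SAP 4.1.5, tables 14.2.1.8 and 14.2.1.16) |
|---|---|---|
| Code after rescue | non-responder | treatment failure, which is the same value |
| Starts | at the time of rescue | at the visit where rescue started |
| Rescue before the Week 16 visit day | Week 16 = 0 | Week 16 = 0 |
| Rescue on the Week 16 visit day, after assessment | Week 16 score may stand | Week 16 = 0 |

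Only the last row separates them at Week 16. For rescue between visits, it makes no difference at Week 16 which earlier visit the start is attached to.

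**2. Coding check.** Both rules were applied to 200,000 simulated patients with visits on days 28, 56, 84 and 112. The assumptions were 20% rescued, a uniform rescue start over days 1 to 112, and a 30% response at each visit independent of rescue.
- Rescue on any non-visit day: 0 differences at any visit.
- Week 16 overall: 0.057% of patients differed, all with rescue on day 112. The expected share is 0.20 × (1/112) × 0.30 = 0.054%.

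The true share is probably smaller. A patient who needs rescue for intolerable symptoms on the Week 16 visit day would rarely be a vIGA-AD 0/1 or EASI-75 responder that day.

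**3. Whether another planned analysis varies the rule.** Jump to reference changes what is assumed after discontinuation and sets no different rescue rule. The PPS is defined by completion and absence of major violations, not by rescue.

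**4. What a different rule could show (illustration only).** The plan's own figure is reproduced first. For 12% v 27%, two-sided 5%, 80% power and pooled variance, the result is 109 per arm after rounding up (the plan's table has 108.4 and the text uses 110). Power at 110 per arm is 80.6%.

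Now take 12% and 27% as the rates with rescue counted as failure. Let r be the proportion rescued in an arm and q the response rate at Week 16 among rescued patients. Counting observed outcomes regardless of rescue gives

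rate = planned rate + r × q.

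Example, with rescue 10% on DS107 and 20% on placebo, and q = 0.40: DS107 0.27 + 0.10 × 0.40 = 0.31; placebo 0.12 + 0.20 × 0.40 = 0.20; difference 11.0 points.

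Power = Φ{[d√n − 1.96√(2p̄(1−p̄))] / √(p₁(1−p₁) + p₂(1−p₂))}. With d = 0.11, n = 110 and p̄ = 0.255, this is 47%.

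| Assumed rescue, DS107/placebo | Difference, q = 0.12 to 0.40 | Power at 110 per arm |
|---|---|---|
| 5% / 10% | 14.4 to 13.0 points | 76% to 64% |
| 10% / 20% | 13.8 to 11.0 points | 71% to 47% |
| 15% / 30% | 13.2 to 9.0 points | 66% to 31% |
| 20% / 20% | 15.0 points throughout | 77% to 71% |

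Every r and q here is assumed. The power figures use the plan's chi-square test, not the GLMM. The table shows only that a different rule could give a visibly different answer or nearly the same one. Tables 14.2.1.8 and 14.2.1.16 cannot tell these cases apart, because they keep the primary coding.

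**The case against.** Several stronger readings are tempting, and the documents do not support them.

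- *The two analyses are identical.* A reader might infer this, but the wording differs. Protocol 9.2.15 asks for assessments immediately before rescue, so a score taken on the day of rescue can stand under one rule and be overwritten under the other. Because the GLMM is longitudinal, such a change at Weeks 4 to 12 could in principle also move the Week 16 estimate. This stands: the rules are the same in effect, not to the letter.
- *Robustness to rescue is never tested.* Some rescue agents are on the prohibited list in protocol 9.2.13.2, and the blind data review (SAP 5) considers the impact of prohibited medications. Some rescued patients may therefore drop out of the PPS. That would be incidental and is not specified as a check on the rescue rule.
- *The primary is simply mislabelled.* The full-adherence sentence is about missing data under MAR, where it fits. A patient given topical rescue may still be taking study drug as directed, so rescue and non-adherence are different events. The mismatch is clearest for systemic rescue: study treatment stops, yet the patient is scored a failure and not modelled as if still treated.
- *The number of rescued placebo patients measures the problem.* If 10% to 20% of 110 were rescued (assumed), that is 11 to 22 patients. At a 12% response, only about 1 to 3 of them (11 × 0.12 = 1.3; 22 × 0.12 = 2.6) would otherwise respond, and a placebo count alone says nothing about the difference between arms.

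The best counter-argument is that the sponsor may have meant rescue as failure only as the sensitivity analysis. The last paragraph of SAP 6.1 again lists it there. On that reading the sentence in SAP 6.1 and protocol 12.8.2 is misplaced, and the estimand label may be right. The documents do not settle this. On either reading they need correcting.

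**Conclusion.** The point holds in this form. Followed as written, the plan yields two sensitivity tables with practically no information on the rescue rule for the Week 16 primary endpoints, and specifies no other analysis that varies it. The full-adherence description does not cover the scoring of rescue as failure.

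The conclusion about the coding rests on the text and on the endpoints being binary. The 0.06% rests on the simulation assumptions. The effect on the treatment difference is unknown because no rescue rate is given, and the ranges above are illustrations, not estimates for this trial.

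If rescue as non-response is the intended primary rule, the primary estimate and the success criterion are unaffected; what is lost is a supportive check and a correct description. If it is not, the primary rule itself is misstated. The matter should be settled before unblinding.

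**What to change.** Reconcile SAP 4.1.5 and 6.1 with protocol 12.8.2, and with the efficacy-analysis sentence in protocol 9.2.15, on which rescue rule the primary analysis uses.

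- **If rescue as non-response stays in the primary:** describe the estimand as composite for rescue and hypothetical (MAR) for other missing data. Redefine 14.2.1.8 and 14.2.1.16 so that they differ from the primary. One version sets post-rescue values to missing and handles them under MAR. A second uses observed vIGA-AD and EASI regardless of rescue, where post-rescue assessments exist.
- **If rescue as failure was meant only as the sensitivity analysis:** remove it from the primary rule in SAP 6.1 and protocol 12.8.2, and state how the primary handles post-rescue data.

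The cost is wording changes in both documents and a small amount of re-programming for tables already planned. Post-rescue data will be incomplete for patients who leave after systemic rescue, so the observed-outcome version should report how many Week 16 values it has in each arm.

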## **4.2 Algorithms for data calculations and modifications**

### **4.2.1 Study Day**

The Study Day of an assessment or event will be defined as

$$\text{Study Day} = \text{Date of Assessment} - \text{Date of first treatment} + 1$$

for assessments performed at/after date of first treatment.

For assessments prior date of first treatment the definition is as follows:

$$\text{Study Day} = \text{Date of Assessment} - \text{Date of first treatment}$$

For patients without treatment, study day will not be calculated.

### **4.2.2 Age**

The age of patients at time of consent [in years] is used as documented in the eCRF.

### **4.2.3 BMI**

The Body Mass Index (BMI) of patients at screening is used as documented in the eCRF.

### **4.2.4 Validated Investigator Global Assessment (vIGA-ADTM)**

The clinical severity of AD will be evaluated by the Investigator at each visit using the vIGA-ADTM scale.

The vIGA-ADTM scale awards a score of 0-4 based on a 5-point severity scale from clear to severe disease (0 = clear, 1 = almost clear, 2 = mild disease, 3 = moderate disease, 4 = severe disease). The scale uses clinical characteristics of erythema, infiltration, papulation and oozing/crusting as scoring guidelines for the overall severity assessment. vIGA-ADTM will be assessed at every clinic visit.

### **4.2.5 Eczema Area Severity Index (EASI)**

EASI quantifies the severity of a patient’s AD based on both lesion severity and the percent of BSA affected (Hanifin et al. 2001). The EASI is a composite score ranging from 0-72 that takes

into account the degree of erythema, induration/papulation, excoriation, and lichenification (each scored from 0 to 3 separately, half points are permitted) for each of four body regions, with adjustment for the percent of BSA involved for each body region and for the proportion of the body region to the whole body.

#### **4.2.6 Pruritus NRS**

Severity of pruritus related to AD will be self-assessed by patients daily using the NRS. Patients will be asked to estimate the intensity of pruritus at its worst over the previous 24 hours. The Pruritus NRS is a single-question assessment tool that will be used to assess the patient's worst itch as a result of AD in the previous 24 hours. Patients will score their pruritus due to AD on a scale of 0 – 10, with 0 (no itch) and 10 (worst itch imaginable) (Phan et al. 2012). Patients will complete the rating scale daily starting at screening through to the last study visit.

The baseline NRS is defined as the prorated average of the NRSs reported continuously for 7 days right before and on the baseline visit (i.e. study day -6 to day 1). For post-baseline NRS, the mean weekly worst itch NRS is calculated as the prorated average of the reported daily NRS within the week. For example, if there are 3 scores in a week, the prorated average = (score1 + score2 + score3)/3.

